#### ***Analysis of infusion associated reaction (IAR)***

- All infusion associated reaction by primary SOC, HLGT, HLT, and PT, showing the number (%) of patients sorted by the internationally agreed SOC order. The other levels (HLGT, HLT, PT) will be presented in alphabetical order
- All infusion associated reaction by primary SOC and PT, showing the number (%) of patients with at least 1 treatment-emergent adverse event, sorted by the internationally agreed SOC order and by decreasing incidence of PTs within each SOC. This sorting order will be applied to all other tables, unless otherwise specified
- By-patient listing of treatment-emergent adverse events of special interest showing analysis group (IAT vs DAT), patient ID, age, gender, race, primary SOC decode, PT decode, verbatim (diagnosis), onset date and study day, date of death (if relevant), recovery date/time, event duration, outcome, intensity/grade, relationship to study treatment, action taken with study treatment AE serious criteria.

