## 9 ASSESSMENT OF INVESTIGATIONAL MEDICINAL PRODUCT

### 9.1 PRIMARY ENDPOINTS: SAFETY

Safety assessments will include the following:

- Incidence, duration, grade/intensity, relationship to study drug, and outcome of the following:
  - Serious Adverse Events (SAEs).
  - Adverse Events (AEs).
  - Infusion-associated reactions (IAR).
- Incidence, nature, seriousness, grade/intensity, relationship to study drug, and outcome of the following project-specific Adverse Events of Special Interest (AESIs):
  - Autoimmune mediated conditions including, but not limited to:
    - Immune thrombocytopenic purpura (ITP).
    - Nephropathies including anti-glomerular basement membrane (GBM) disease.
    - Cytopenias.
    - Thyroid disorders.
    - Acquired hemophilia A
    - Autoimmune hepatitis.
    - Hemophagocytic lymphohistiocytosis (HLH).
    - Progressive multifocal leukoencephalopathy (PML)
    - Temporally associated\* pulmonary alveolar hemorrhage
    - Temporally associated\* myocardial ischemia, myocardial infarction
    - Temporally associated\* stroke
    - Temporally associated\* cervicocephalic arterial dissection(\* Temporally associated: 1 to 3 days after the last infusion)
  - Serious infections including serious opportunistic infections (eg, Listeria infections, CMV, EBV), HPV associated with cervical dysplasia
  - Malignancy.
  - Pneumonitis
- Changes in laboratory parameters.

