#### **2.1.4.1 Adverse events variables**

All adverse events will be coded to a lower-level term (LLT), preferred term (PT), high-level term (HLT), high-level group term (HLGT), and associated primary system organ class (SOC) using the version of Medical Dictionary for Regulatory Activities (MedDRA) currently in effect at Sanofi at the time of database lock OR specify version if already known from project specifics.

Incidence, duration, grade/intensity, relationship to study drug, and outcome of the AE will be analyzed for serious adverse events (SAEs), adverse events (AEs), infusion-associated reactions (IAR).

Incidence, nature, seriousness, grade/intensity, relationship to study drug, and outcome will be summarized for the project-specific adverse events of special interest (AESIs).

Record the occurrence of adverse events (including serious adverse events and adverse events of special interest) from the time of signed informed consent until the end of the study.

**Adverse events of special interest** include the following terms:

- Hypersensitivity or anaphylaxis
- Pregnancy of a woman entered in the study;

- Pregnancy occurring in a woman patient entered in the clinical trial. It will be qualified as an SAE only if it fulfills one of the seriousness criteria.
- Follow-up of the pregnancy in a woman participant is mandatory until the outcome has been determined.
- Symptomatic overdose (serious or non-serious) with IMP.
  - An overdose (accidental or intentional) with the IMP is an event suspected by the Study Investigator or spontaneously notified by the patient and defined as increase of at least 30% of the dose to be administered in the specified duration or if the dose is administered in less than half the recommended duration of administration.  
  
Of note, asymptomatic overdose must be reported as a standard AE.
- Increase in alanine transaminase (ALT).
- Other product specific AESIs:
  - Autoimmune mediated conditions including, but not limited to:
    - Immune thrombocytopenic purpura (ITP).
    - Nephropathies including anti-glomerular basement membrane (GBM) disease.
    - Cytopenias.
    - Thyroid disorders.
    - Acquired hemophilia A
    - Autoimmune hepatitis.
  - Hemophagocytic lymphohistiocytosis (HLH).
  - Progressive multifocal leukoencephalopathy (PML)
  - Temporally associated\* pulmonary alveolar hemorrhage
  - Temporally associated\* myocardial ischemia, myocardial infarction
  - Temporally associated\* stroke

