  - Temporally associated\* cervicocephalic arterial dissection  
(\* Temporally associated: 1 to 3 days after the last infusion)
  - Serious infections including serious opportunistic infections (eg, Listeria infections, CMV, EBV), HPV associated with cervical dysplasia
  - Malignancy.
  - Pneumonitis

The standardized MedDRA queries (SMQ) or Custom MedDRA queries (CMQ) will be applied as appropriate to select AESIs.

**Infusion-associated reactions (IAR)** is defined as any adverse event occurring during and within 24 hours of alemtuzumab infusion. It will be analyzed separately for retreated patients.

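### The SAP's infusion-reaction section tabulates incidence only, and the one listing there that would show duration, intensity, relationship and outcome is titled as a listing of AESIs

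*SAP*

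**What the plan says.** Protocol 9.1 lists three classes of event under the primary safety endpoint (SAEs, AEs and IARs) and asks for the "Incidence, duration, grade/intensity, relationship to study drug, and outcome of the following" classes. SAP 2.1.4.1 takes this over: "Incidence, duration, grade/intensity, relationship to study drug, and outcome of the AE will be analyzed" for the same three classes. It defines an IAR as any adverse event during an alemtuzumab infusion or within a day of it, and adds: "It will be analyzed separately for retreated patients".

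The IAR part of SAP 2.4.5.1 has three items:

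- "All infusion associated reaction by primary SOC, HLGT, HLT, and PT, showing the number (%) of patients"
- "All infusion associated reaction by primary SOC and PT, showing the number (%) of patients with at least 1 treatment-emergent adverse event"
- "By-patient listing of treatment-emergent adverse events of special interest showing analysis group (IAT vs DAT), patient ID, age, gender, race", followed by further columns that include duration, outcome, intensity and relationship.

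**The concern.** The endpoint sections promise a separate IAR analysis with five attributes. The section meant to deliver it specifies incidence tables and a listing of a different class of event. A programmer who follows the text would produce a second AESI listing and no IAR listing. The report could then say how many re-treated patients had an infusion reaction. For ordinary reactions, it would not show as a group how intense they were, how long they lasted, whether they were judged related, or how they ended.

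This matters because IARs are one of the three event classes in the primary endpoint, and because the two most recent protocol amendments tightened infusion management. The tolerability of re-treatment infusions is something a reader will expect this study to describe.

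**Working it through.** No arithmetic beyond counting applies. The check sets the promised attributes against the planned outputs.

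**Step 1. Attributes against outputs.** The inputs are Protocol 9.1, SAP 2.1.4.1, all parts of SAP 2.4.5.1, and SAP 2.4.5.2.

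| Attribute | IAR-specific table | IAR-section listing, read literally | Same listing, if retitled | Outputs not specific to IARs |
|---|---|---|---|---|
| Incidence | Yes, two tables | AESIs only | Per patient | All-TEAE tables |
| Duration | None | AESIs only | Per patient | Listings of SAEs, discontinuations and AESIs |
| Intensity | None | AESIs only | Per patient | Those listings; all-TEAE table by maximal severity |
| Relationship | None | AESIs only | Per patient | Those listings; relationship tables for all TEAEs and for serious TEAEs |
| Outcome | None | AESIs only | Per patient | Those listings; fatal outcome tabulated for all TEAEs |

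One of five attributes has an IAR-specific summary, so 5 − 1 = 4 have none. This count is the same whether or not the listing title is a slip.

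**Step 2. Is the listing in the IAR section really an AESI listing?** The AESI part of SAP 2.4.5.1 ends with its own by-patient listing. That one has columns for the number of alemtuzumab courses and for the AESI group. The listing in the IAR section has neither, and its remaining columns are the same. A second AESI listing without the AESI group would serve little purpose. With its position under the IAR heading, this points to an IAR listing that kept a copied title.

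**Step 3. Which IARs have no listing if the title is followed literally?** The SAP specifies by-patient adverse event listings for three sets: serious events, events leading to treatment discontinuation, and AESIs. An IAR in any of these sets is listed with duration, outcome, intensity and relationship. An IAR in none of them is not listed.

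That remainder is unlikely to be empty. Protocol section 4 names headache and pyrexia among the most common events after alemtuzumab (20% or more of patients), and neither is on the AESI list in SAP 2.1.4.1. Rash, also named there, is less clear: it might be captured under hypersensitivity, depending on MedDRA queries whose contents the SAP does not show. The 20% describes adverse events after treatment in general, so it does not give the number of IARs affected.

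**Step 4. Do the general tables fill the gap?** SAP 2.4.5.1 counts every reported adverse event as treatment-emergent. IARs therefore enter the severity and relationship tables, but together with everything else reported over the study. IAR intensity or relationship cannot be read off those tables. No table covers duration, or any outcome other than death.

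**The case against.** The strongest reply is that this is a slip in one title. The listing stands under the IAR heading and carries all four attributes, and SAP 2.1.4.1 commits to analysing them. Protocol 11.4 also promises, in general terms, that all data will be reported in tables, figures and patient listings. This stands to the extent that a reader might infer that these IAR attributes are never produced, or that the listing merely repeats the AESI one. The documents support neither: the columns differ from those of the AESI listing, and many IARs are listed elsewhere.

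A reader might also infer that the serious infusion events behind the amendments go unreported. They do not. Temporally associated stroke, myocardial ischemia or infarction, arterial dissection and pulmonary alveolar hemorrhage are AESIs. They have their own table by infusion day and following days in the retreated population, and they appear in the AESI listing. Hypersensitivity and anaphylaxis are AESIs too.

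A further reply is that SAEs fall under the same five attributes, yet the SAP gives their duration, intensity and outcome mainly through a listing. A retitled IAR listing would put IARs on much the same footing for those three. This is fair, and it makes the extra table the less pressing half of the fix. It does not remove the need for it. SAEs get a relationship table and IARs do not, and the SAP promises IARs a separate analysis, for which a listing alone is thin.

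Finally, the study is descriptive, without formal hypothesis tests. No estimate, denominator or data collection is wrong because of this point.

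**Conclusion.** The point holds in a limited form. SAP 2.4.5.1 has no IAR-specific summary of duration, intensity, relationship or outcome, although all four belong to the primary IAR endpoint. The only listing in that section that would show them is titled as AESIs, probably by copy error.

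On a literal reading, the listing gap is confined to IARs that are non-serious, are not AESIs and did not lead to discontinuation. If the title is a slip, that gap closes once it is corrected, but the missing summaries remain. How many events are involved cannot be stated, because the documents give neither the number of patients re-treated in this study nor an IAR rate.

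This deserves correction before the tables are programmed. It is more than editorial, because the stated output rule yields the wrong listing for a primary-endpoint event class. It does not threaten the study's conclusions on the serious infusion events.

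**What to change.** In the IAR part of SAP 2.4.5.1:

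1. Retitle the by-patient listing to infusion-associated reactions in the retreated population.
2. Add one IAR table in the retreated population by maximal intensity, relationship to study drug, outcome and duration. Since SAP 2.5.2 does not impute adverse event end dates, the table should show how many IARs have no duration available.

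A breakdown by course or infusion day is optional. The endpoint does not ask for it, although the SAP already uses infusion-day intervals for the temporally associated AESIs.

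The cost is one corrected listing and one extra table. Protocol 10.4.2 already requires onset date, intensity, outcome and causality, and the listing already assumes recovery date and duration. No new data are needed, and sample size and inference are unaffected.

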#### **2.4.5.2 Deaths**

The following summaries of deaths will be generated for the safety population.

- Number (%) of patients who died by study period (on-study, poststudy)
- Deaths in nonrandomized patients or randomized but not treated patients
- Treatment-emergent adverse events leading to death (death as an outcome on the adverse event case report form page as reported by the Investigator) by primary SOC , HLGT, HLT, and PT showing number (%) of patients sorted by internationally agreed SOC order, with HLGT, HLT, and PT presented in alphabetical order within each SOC .

#### **2.4.5.3 Analyses of laboratory variables**

Laboratory analysis will be conducted for retreated population and 48 months follow-up population. The baselines for each population are defined as below.

- Retreated population baseline: The last non-missing assessment prior to first dose of alemtuzumab in TOPAZ study. The baseline should be taken within 2 weeks prior to the treatment for laboratory assessment except for HPV and pregnancy test. For HPV and pregnancy test, it can be taken in 12 months before the treatment.
- 48 months follow-up population baseline: The last non-missing assessment prior to the last dose of alemtuzumab in previous studies. The baseline should be taken within 2 weeks

prior to the treatment for laboratory assessment except for HPV and pregnancy test. For HPV and pregnancy test, it can be taken in 12 months before the treatment.

The summary statistics (including number, mean, median, Q1, Q3, standard deviation, minimum and maximum) of all laboratory variables (central laboratory values and changes from baseline) will be calculated for each visit or study assessment (baseline, each postbaseline time point, last on-treatment and/or worst on-treatment value and/or other specific assessment) in overall group and by subgroups (IAT vs DAT). This section will be organized by biological function [Section 2.1.4.3](#).

The incidence of PCSAs (list provided in [Appendix A](#)) at any time during the treatment-emergent adverse event period will be summarized by biological function and in overall group and by subgroups (IAT vs DAT) whatever the baseline level and/or according to the following baseline status categories:

- Normal/missing
- Abnormal according to PCSA criterion or criteria

For parameters for which no PCSA criteria are defined, similar table(s) using the normal range will be provided.

#### ***Drug-induced liver injury***

The liver function tests, namely AST, ALT, alkaline phosphatase, direct bilirubin and total bilirubin, are used to assess possible drug-induced liver toxicity. The proportion of patients with PCSA values at any postbaseline visit by baseline status will be displayed in overall group and by subgroups (IAT vs DAT) for each parameter.

Time to onset of the initial ALT and AST elevation ( $>3$  x ULN) and total bilirubin elevation ( $>2$  x ULN) (time to first observation of ALT  $> 3$  x ULN or total bilirubin  $> 2$  x ULN, whichever comes first) will be analyzed using Kaplan-Meier estimates, using the midpoint of the time interval between the first assessment showing the elevation and the previous assessment, presented in overall group and by subgroups (IAT vs DAT).

Listing of possible Hy's law cases identified (eg, patients with any elevated ALT $>3$  x ULN, and associated with an increase in bilirubin  $\geq 2$  x ULN) with ALT, AST, alkaline phosphatase and total bilirubin.

Summarize the incidence of liver-related adverse events in overall group and by subgroups (IAT vs DAT). The selection of preferred terms will be based on the hepatic disorder SMQ.

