## Appendix A Potentially clinically significant abnormalities criteria

### CRITERIA for POTENTIALLY CLINICALLY SIGNIFICANT ABNORMALITIES for Phase 2/3 studies (oncology excepted) (Version 3.0 May 2014)

Parameter	PCSA	Comments
Clinical Chemistry		
ALT	By distribution analysis : >3 ULN >5 ULN >10 ULN >20 ULN	Enzymes activities must be expressed in ULN, not in IU/L. Concept paper on DILI - FDA draft Guidance Oct 2007. Internal DILI WG Oct 2008. Categories are cumulative. First row is mandatory. Rows following one mentioning zero can be deleted.
AST	By distribution analysis : >3 ULN >5 ULN >10 ULN >20 ULN	Enzymes activities must be expressed in ULN, not in IU/L. Concept paper on DILI – FDA draft Guidance Oct 2007. Internal DILI WG Oct 2008. Categories are cumulative. First row is mandatory. Rows following one mentioning zero can be deleted.
Alkaline Phosphatase	>1.5 ULN	Enzymes activities must be expressed in ULN, not in IU/L. Concept paper on DILI – FDA draft Guidance Oct 2007. Internal DILI WG Oct 2008.
Total Bilirubin	>1.5 ULN >2 ULN	Must be expressed in ULN, not in µmol/L or mg/L. Categories are cumulative. Concept paper on DILI - FDA draft Guidance Oct 2007. Internal DILI WG Oct 2008.
Conjugated Bilirubin	>35% Total Bilirubin and TBILI>1.5 ULN	Conjugated bilirubin dosed on a case-by-case basis.
ALT and Total Bilirubin	ALT>3 ULN and TBILI>2 ULN	Concept paper on DILI - FDA draft Guidance Oct 2007. Internal DILI WG Oct 2008. To be counted within a same treatment phase, whatever the interval between measurements.

**CRITERIA for POTENTIALLY CLINICALLY SIGNIFICANT ABNORMALITIES  
for Phase 2/3 studies (oncology excepted)  
(Version 3.0 May 2014)**

Parameter	PCSA	Comments
CPK	>3 ULN >10 ULN	FDA Feb 2005. Am J Cardiol April 2006. Categories are cumulative. First row is mandatory. Rows following one mentioning zero can be deleted.
CrCl (mL/min) (Estimated creatinine clearance based on the Cockcroft-Gault equation)	<15 (end stage renal disease) ≥15 - <30 (severe decrease in GFR) ≥30 - < 60 (moderate decrease in GFR) ≥60 - <90 (mild decrease in GFR) ≥90 (normal GFR)	FDA draft Guidance 2010 Pharmacokinetics in patients with impaired renal function-study design, data analysis, and impact on dosing and labeling

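### The liver time-to-onset analysis is announced for ALT, AST and total bilirubin, but its event rule leaves AST out

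*SAP*

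**What the plan says.** The liver subsection of SAP 2.4.5.3 lists AST, ALT, alkaline phosphatase and direct and total bilirubin as tests that "are used to assess possible drug-induced liver toxicity". It plans four outputs:

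- **Abnormality tables.** "The proportion of patients with PCSA values at any postbaseline visit by baseline status will be displayed in overall group" and by IAT/DAT subgroup, for each parameter, so AST is included.
- **Time to onset.** The sentence opens with "Time to onset of the initial ALT and AST elevation", sets 3 x ULN for the enzymes, and adds total bilirubin above 2 x ULN. Its bracket then gives the working definition: "time to first observation of ALT" above 3 x ULN or of total bilirubin above 2 x ULN, "whichever comes first". Onset is dated "using the midpoint of the time interval between the first assessment showing the elevation and the previous assessment".
- **Hy's law listing.** Possible cases are selected on ALT with bilirubin, and AST is among the values displayed.
- **Liver-related adverse events**, selected by the hepatic disorder SMQ.

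SAP Appendix A gives AST the same thresholds as ALT: 3, 5, 10 and 20 x ULN. Protocol 9.5.2.2 and 10.1.6.2 require AST monthly, within the liver panel, for 48 months after the last infusion in re-treated patients.

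**The concern.** The announcement and the event rule disagree within one sentence. The announcement covers three markers and the rule uses two. Someone programming the bracket ignores AST. Someone programming the announcement might build a three-marker composite, run separate analyses, or require ALT and AST to be raised together. These choices give different event counts and onset dates, overall and for IAT versus DAT.

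Safety is the primary endpoint, laboratory changes are listed under it in Protocol 9.1, and Protocol 10.1.6 ties the liver tests to monitoring for autoimmune hepatitis. The abnormality tables show whether a threshold was ever crossed. Among the laboratory liver outputs, only this analysis estimates when. If AST is left out, that estimate uses less than the SAP says it will.

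**Working it through.** The SAP states no figure for this analysis, so there is none to reproduce. The check has three parts.

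**1. Which patients count.** The table lists the eight yes/no patterns of ALT above 3 x ULN, AST above 3 x ULN and total bilirubin above 2 x ULN. It compares the announced scope (any of the three) with the bracketed rule (ALT or bilirubin).

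| Elevated | Announced scope | Bracketed rule | Onset date under the rule |
|---|---|---|---|
| None | no event | no event | – |
| ALT only | event | event | same |
| AST only | event | **censored** | – |
| Bilirubin only | event | event | same |
| ALT + AST | event | event | later if AST rose first |
| ALT + bilirubin | event | event | same |
| AST + bilirubin | event | event | later if AST rose first |
| All three | event | event | later if AST rose first |

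Seven patterns carry an announced elevation. The rule counts six and misses AST only. In three of the six, the date can be late. These are counts of logical patterns, not of patients.

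**2. Direction.** Let T be the first elevated assessment for each marker.

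- Rule: min(T_ALT, T_bili).
- Announced scope: min(T_ALT, T_AST, T_bili).

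A minimum over more markers is never larger. With the markers measured on one panel, the rule therefore cannot produce an earlier onset or an extra event. On a monthly schedule the midpoint convention dates an elevation first seen at month k to k − 0.5. If AST crosses at month k and the first of ALT or bilirubin at month k + m, the recorded onset is (k + m − 0.5) − (k − 0.5) = m months late.

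**3. Size, on assumed rates.** The documents give no rates. Assume that 3% of patients reach the ALT threshold (with or without other markers), 0.5% the AST threshold only, and 1% to 2% the bilirubin threshold only. Assume also that none have AST with bilirubin but without ALT, and ignore censoring.

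- Bracketed rule: 3% + 1% = 4%, to 3% + 2% = 5%.
- Announced scope: 3% + 0.5% + 1% = 4.5%, to 3% + 0.5% + 2% = 5.5%.
- Shortfall: 0.5 percentage points, the AST-only share. In relative terms this is 0.5/5.5 = 9% to 0.5/4.5 = 11%.

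**The case against.** The best defence is that the bracket is the intended definition and the mention of AST is stray wording. ALT is the index enzyme elsewhere: the ALT adverse event of special interest, the protocol's medically important event, the Hy's law listing, and the combined Appendix A criterion "ALT>3 ULN and TBILI>2 ULN". That reading is possible. It would still require an edit, because the announcement would then promise an analysis of AST that is not done.

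It is also fair to say that little depends on this curve. Autoimmune hepatitis is itself an adverse event of special interest, with its own tables, rates and a listing that carries onset dates. Liver-related events are summarised by SMQ. SAP 2.4.5 plans no systematic testing of safety variables. All of this stands and keeps the point minor.

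A reader might infer three stronger things that the documents do not support:

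- **That AST elevations are ignored altogether.** They are missing from this event rule only. The abnormality tables and the Hy's law listing include AST.
- **That counting an isolated bilirubin rise is an error.** Bilirubin is named in the announcement and in the bracket, which agree on it. The SAP calls the event an elevation, not an onset of liver injury. A mixed curve is harder to interpret, but that is not a contradiction.
- **That the rule inflates incidence.** On the assumed rates, 4% to 5% exceeds a transaminase-only figure of 3% + 0.5% = 3.5% by 14% to 43%. That comparator drops bilirubin, which the SAP announces. Against the announced scope the direction is downward.

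The Hy's law listing uses bilirubin at or above 2 x ULN where Appendix A uses strictly above. This sits in an example of possible cases and matters only for a value exactly at the threshold.

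**Conclusion.** The inconsistency is real, and it is confined to one sentence and one descriptive analysis. As written, AST-only patients are censored and AST-first patients receive a later onset date, so the result can only understate incidence or delay onset relative to what the SAP announces. The incidence shortfall equals the share of patients with an AST elevation alone. On the assumed rates that is 0.5 percentage points, or 9% to 11% in relative terms. The text establishes the direction. The size is illustrative and rests entirely on those assumptions. No hypothesis test, sample size or primary conclusion is affected. This is a minor point, but worth correcting before the final analysis because it changes which patients have events and when.

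**What to change.** Make the event rule in SAP 2.4.5.3 match its announcement. Define the event as the first of ALT above 3 x ULN, AST above 3 x ULN or total bilirubin above 2 x ULN, and label it a composite. Preferably also show two separate Kaplan-Meier curves, one for first ALT or AST above 3 x ULN and one for first total bilirubin above 2 x ULN, so that the component driving onset is visible. If the sponsor does intend ALT as the only enzyme, it should remove AST from the announcement and say so.

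The cost is SAP wording and at most one extra figure. Where AST is already measured on the liver panel, no new data are needed.
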